7. DESIGN

The study will be a prospective randomized double-blind placebo-controlled trial of mirabegron for MET in patients with a CT scan or Ultrasound/KUB-proven ureteral stone between 4 to 10 mm undergoing expectant management. Subjects will be distributed at a 1:1 ratio between the control and treatment groups. The treatment group will receive mirabegron and the control groups will receive a placebo. Both groups will receive analgesics and hydration will be recommended. All subjects will then be followed for 30 days to determine the proportion of subjects with spontaneous passage. Patients will record narcotic usage and pain scores during

this time. If there is stone persistence in the ureter based on imaging (CT scan or Ultrasound/KUB of the abdomen and pelvic, then the patient will undergo ureteroscopy with stent placement. In these patients, treatment will continue while the stent is in place and patients will fill out a validated questionnaire regarding stent pain.

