11. SAMPLE SIZE

The primary outcome measure is spontaneous stone passage. The proportion of patients who spontaneously pass the stone within 30 days will be compared between the mirabegron and placebo groups using Fisher's exact test. Previous research suggests that about 50% of subjects in the placebo group will have a spontaneous stone passage. A sample size of 45 subjects per group will provide 80% power to detect a 0.30 unit difference in proportions using Fisher's exact test assuming alpha=0.05 and half of the patients in the placebo group have spontaneous stone passage. Therefore, a total of 104 subjects will be enrolled into this study to allow for 15% attrition.

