13. DATA ANALYSIS

Patient demographics and clinical characteristics will be summarized by means with standard deviations, medians with minimum and maximum values, or frequencies with percentages. Summary statistics will be stratified by treatment group. No univariable analysis will be completed in this randomized clinical trial.

The primary analysis will compare the proportion of subjects with spontaneous stone passage within 30 days between study groups using Fisher's exact test. Statistical significance will be assessed at the 0.05 level (two-sided). A logistic regression model will also be used to estimate the odds ratio for spontaneous stone passage in the mirabegron group versus the placebo with a 95% confidence interval.

A multiple logistic regression model, adjusting for treatment group, will also be used to test for significant associations between spontaneous stone passage and patient demographics or clinical characteristics. Parameter estimates significant at the 0.05 level will be included in the final multiple regression model. No adjustments will be made for multiple hypothesis testing.

A secondary objective of this study is to compare pain measures between treatment groups. The Wong Baker FACES pain scale will be measured daily for each patient. A general linear mixed model will be used to compare pain scores between treated and placebo groups. The model will include fixed effects for treatment group, time (discrete) and a group-time interaction term. The matrix of correlated residual terms will assume an unstructured format. This model will account for the correlation between repeated measures within the same subject and will allow for all available data to be included in the model.

Missing data will not be imputed. Model fit will be assessed using influence diagnostics and residual analysis. Data transformations (e.g., natural logarithm) will be used if departure from model assumptions is evident. The model will also be used to explore associations between pain scores and demographic and clinical characteristics, adjusting for treatment group and time.

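### Boschloo's exact test would give the primary comparison slightly more power than Fisher's at no cost: about 2 points on average, 4.4 at exactly 45 per arm (an improvement, not an error)

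*Combined protocol and SAP*

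**What the plan says.** Section 13 makes the primary analysis a comparison of the proportion with spontaneous stone passage "within 30 days between study groups using Fisher's exact test". The level is 0.05, two-sided.

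Section 11 uses the same test for the sample size: "A sample size of 45 subjects per group will provide 80% power to detect a 0.30 unit difference in proportions using Fisher's exact test". The placebo rate is taken as about 50%, so the design alternative is 80% v 50%. Enrolment is set so that "a total of 104 subjects will be enrolled into this study to allow for 15% attrition", and Section 7 allocates 1:1.

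Section 13 adds a second summary of the same comparison: "A logistic regression model will also be used to estimate the odds ratio for spontaneous stone passage", with a 95% confidence interval. It does not name the interval method. It calls the Fisher comparison primary, but does not say how to report a p-value and an interval that point different ways. No unconditional or mid-p test is mentioned.

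**The concern.** Fisher's test conditions on the total number of passages. With arms of this size its p-value moves in coarse steps, so the true type I error can sit well below the nominal 5%. Stone passage is the only endpoint with a power calculation, so any level left unused there is power that could be had without more patients.

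There is also a matter of coherence. A Wald interval for the odds ratio runs closer to 5% than Fisher's test does. The trial could therefore report a non-significant primary p-value next to an interval that excludes 1.

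**Working it through.** **Inputs.** Placebo rate 0.50, difference 0.30, 45 per group, 104 enrolled, 15% attrition (Section 11); 1:1 allocation (Section 7); two-sided 0.05 and Fisher's test (Section 13).

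**Formulas.** With arm sizes n1, n2, passages x, y and total s = x + y, let h(k) = C(n1,k)·C(n2,s−k)/C(n1+n2,s).
- Two-sided Fisher: p(x,y) = sum of h(k) over all k with h(k) ≤ h(x).
- Power: sum over all tables of Bin(x; n1, p1)·Bin(y; n2, p2) where the test rejects. Size is the same sum with p1 = p2, maximised over a fine grid of common rates.
- Boschloo: reject when p(x,y) ≤ c, where c is the largest cut-off that keeps the maximum size at or below 0.05. Fisher's own size never exceeds 0.05, so c is at least 0.05. Every table that Fisher rejects is rejected here too, so power cannot be lower.

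**The plan's own figure.** At 45 v 45 and 80% v 50%, Fisher's exact power is 81.5%. The stated 80% is met.

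**Size at 45 v 45.** Fisher: 2.7%, 3.2% and 2.6% at common rates 0.50, 0.65 and 0.80; maximum 3.2%. Boschloo: c = 0.0751, maximum size 4.9%.

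**Power at 80% v 50% (treatment arm first).**

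| Analysed | Fisher | Boschloo | Gain (points) | Fisher max size |
|---|---|---|---|---|
| 45 v 45 | 81.5% | 85.9% | 4.4 | 3.2% |
| 44 v 44 | 80.2% | 84.9% | 4.7 | 3.1% |
| 40 v 40 | 74.9% | 81.0% | 6.0 | 3.3% |
| 52 v 52 | 86.9% | 90.6% | 3.7 | 3.9% |
| 45 v 44 | 84.4% | 85.6% | 1.2 | 4.0% |
| 46 v 43 | 82.8% | 85.3% | 2.5 | 3.8% |
| 47 v 42 | 83.5% | 84.1% | 0.6 | 3.9% |

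Equal arms are the case least favourable to Fisher, so the gain has to be averaged over the arm sizes that the trial is likely to analyse.

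**Averaging over attrition.** Assume 104/2 = 52 randomised per arm and each subject lost independently with probability 0.15, so each analysed arm is Bin(52, 0.85). Arm sizes 38 to 50 in both arms hold 98% of the probability. Weighted over these:
- Fisher's maximum size averages 3.9%.
- At 80% v 50%, power is 82.6% for Fisher and 84.7% for Boschloo, a gain of 2.0 points before rounding. Single pairs of arm sizes range from about 0 to 6 points. The gain reaches 4 points in about 11% of trials, and the arms are equal in about 11%.
- At 70% v 50%, power is 43.5% against 47.8%, a gain of about 4 points (40.9% against 47.6% at exactly 45 v 45).

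**Conflict with the odds-ratio interval (Wald assumed).** Take 36/45 v 27/45. OR = (36×18)/(27×9) = 2.67. SE of log OR = √(1/36 + 1/9 + 1/27 + 1/18) = 0.481. The 95% CI is exp(0.981 ± 1.96×0.481) = 1.04 to 6.85. Fisher's p is 0.065; Boschloo's is 0.045.

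The chance at 80% v 50% that the interval excludes 1 while the test does not reject:
- 45 v 45: 4.3% with Fisher, about 0.0% with Boschloo.
- 44 v 44: 5.5% and 0.8%.
- 46 v 43: 4.2% and 1.8%.
- Averaged over attrition: about 2.6% and 0.8%.

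**The case against.** The strongest reply is that nothing is wrong. Sections 11 and 13 name the same test, the conservatism is already paid for in the 45 per group, the stated power is met, and type I error stays below 5%. All of that stands. A reader might infer from a true size near 3% that the trial is underpowered or its calculation mistaken; the documents do not support that.

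A reader might also take the 45 v 45 figures as the trial's figures: only about 3% of alpha used, over 4 points of power given up, and about 86% available. Those figures depend on equal analysed arms. Section 11 plans for 15% attrition, and on the assumption above the arms are equal in only about one trial in nine.

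Three further objections hold in part:
- **Two-sided version.** Boschloo's test has more than one. The function in scipy does not order by the two-sided Fisher p-value, and with unequal arms it can miss a result that Fisher finds: for 43/45 v 36/44, Fisher gives 0.0496 and that function 0.056. The guarantee of never being less powerful belongs only to the ordering used here, so the plan must name it.
- **Interval conflict.** Section 13 names no interval method, so the conflict rests on assuming Wald. Section 13 does make Fisher primary, which suggests that its p-value governs, but does not say so for a disagreement. The change makes disagreement rarer; a reader who expects it to disappear is generalising from 45 v 45.
- **Stratification.** Boschloo's test, like Fisher's, ignores the strata used in randomisation. That is a separate question and this change does not settle it.

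**Conclusion.** The point holds as an optional improvement at no cost, not as an error. Fisher's test is valid here and delivers the promised 80%. Boschloo's test ordered by the two-sided Fisher p-value is also exact, is never less powerful, and gains about 2 points on average at the design alternative and about 4 at 70% v 50%.

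The averages assume 52 randomised per arm, independent 15% loss at the same rate in both arms, and exclusion of lost subjects from the primary comparison. If all 104 were analysed as 52 v 52, the gain would be 3.7 points. The conflict rates assume an unadjusted logistic model with a Wald interval. The results do not support cutting the sample size, or stating 86% power without the condition of exactly 45 v 45.

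**What to change.** In Sections 11 and 13, replace the primary test with: *Boschloo's unconditional exact test, two-sided 0.05, tables ordered by the two-sided Fisher p-value.*

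- Keep 45 per group and the total of 104.
- Leave the power statement at *at least 80%*, or give about 86% for exactly 45 v 45 and about 85% allowing for attrition.
- Add to Section 13 that this p-value decides significance, and name the method for the odds-ratio interval.
- Report Fisher's p-value as a sensitivity result.
- Check that the software uses the named ordering when the arms are unequal.

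The cost is a few sentences, settled before unblinding, and a short check of the program. No patients, visits or data are added. If the sponsor prefers to keep Fisher's test, the least that is useful is a sentence saying that its p-value governs, with an interval consistent with it.

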8. RANDOMIZATION

Study participants will be randomized to the treated arm (mirabegron 50 mg orally once every 24 hours starting immediately) or placebo in a 1:1 ratio using a randomized block design, stratified by stone size (≤ 5 mm versus > 5 mm) and location (upper versus lower ureter). The randomization will be implemented through a database with software designed by the Director of Research Informatics at the Baylor College of Medicine's (BCM) Dan Duncan Institute of Clinical and Translational Research. It will be a HIPPA-compliant secure database accessible via internet.

Each randomly assigned participant will be given 60 capsules of trial medication (over-encapsulated mirabegron or placebo) supplied by Astellas Pharm US, Inc. and dispensed by the Harris Health System Pharmacy. Both Astellas Pharm US, Inc. and Harris Health Pharmacy will have no further involvement in the trial, ensuring that participants, clinicians, and trial personnel remained unaware of the allocated group.

Justification:

Two decades ago, the first randomized trial demonstrating the potential efficacy of a calcium channel blocker (nifedipine) for medical expulsive therapy of ureteral stones was performed.³ Subsequently, tamsulosin, a selective alpha-1a antagonist, has also been demonstrated as a potentially useful agent for MET in randomized trials.⁴ Over the past decade, off-label MET has become more commonplace. However, the strength of findings from randomized trials is weak due to variability in quality and power of study design.

In 2015, a large multi-center randomized placebo-controlled trial (SUSPEND Trial) included 1167 patients and compared the efficacy of nifedipine and tamsulosin for the reduction in surgical therapy in patients passing ureteral stones within 4 weeks after randomization.⁵ This trial demonstrated that both nifedipine and tamsulosin were ineffective for MET and were associated with an increase in adverse effects compared to placebo. These findings suggest that current off-label therapy with calcium-channel blockers and alpha-blockers may be ineffective and inappropriate. Because ureteral stones remain an important and expensive medical problem, identification of other potential agents for MET may reduce the frequency of serious complications and necessity of surgical intervention as well as improve patient-centered outcomes.

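### In the supporting multiple logistic model for stone passage, the p < 0.05 inclusion rule can drop the randomisation strata and overstates the odds ratios of weak to moderate covariates it keeps

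*Combined protocol and SAP*

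**What the plan says.** Section 13 (Data Analysis) describes three separate analyses of stone passage.

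1. The primary test: "The primary analysis will compare the proportion of subjects with spontaneous stone passage within 30 days between study groups using Fisher's exact test".
2. A treatment estimate: "A logistic regression model will also be used to estimate the odds ratio for spontaneous stone passage in the mirabegron group versus the placebo". It is to carry an interval at the 95% level, and no covariates are named for it.
3. A covariate model, which relates passage to features of the subjects that are described only in general terms: "A multiple logistic regression model, adjusting for treatment group, will also be used to test for significant associations between spontaneous stone passage and" (the features follow).

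The selection rule follows the third analysis: "Parameter estimates significant at the 0.05 level will be included in the final multiple regression model". Section 13 names no candidate covariates for this model and makes no adjustment for multiple testing. Treatment group is adjusted for, and no other term is protected.

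Section 8 (Randomization) says that allocation is "stratified by stone size (≤ 5 mm versus > 5 mm) and location (upper versus lower ureter". Section 12 lists possible covariates, but for the two pain analyses and not for stone passage.

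**The concern.** The rule uses the trial's own outcome data to choose the model and then reports that model as final. With about 90 subjects this has two effects. A real but moderate predictor often misses p < 0.05 and is removed. When it is kept, that is partly because its estimate came out high in this sample, so the reported odds ratio is too large on average. A candidate with no effect can also enter by chance.

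Stone size and location matter most here. The trial stratifies on them, and Section 1 says that passage varies with both. Yet no pre-specified analysis of stone passage is sure to contain them: the Fisher test is unstratified, the treatment model names no covariates, and the third model may delete them. What is at stake is the trial's account of which characteristics predict passage, which is the purpose of this model.

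**Working it through.** **The plan's own figure.** Section 11 assumes that "Previous research suggests that about 50% of subjects in the placebo group will have a spontaneous stone passage" and states that "A sample size of 45 subjects per group will provide 80% power to detect a 0.30 unit difference in proportions using Fisher's exact test". Take p = 0.50 and 0.80, with mean 0.65:

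- n = [1.96 √(2 × 0.65 × 0.35) + 0.842 √(0.25 + 0.16)]² / 0.30² = 38.5, so 39 per group. The continuity correction raises this to 45.
- Exact two-sided Fisher power is 0.815 at 45 per group and 0.802 at 44.
- For enrolment, 90 × 1.15 = 103.5, so 104.

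The sample size reproduces, and the check below uses 90 evaluable subjects. Expected non-passers are 45 × 0.50 + 45 × 0.20 = 31.5. A seven-term model therefore has 31.5 / 7 = 4.5 per term.

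**What the documents say about prognosis.** Section 1 gives 47-80% passage depending on size and location. Between the extremes the odds ratio is (0.80/0.20) / (0.47/0.53) = 4.51. Split equally over two factors, it is √4.51 = 2.12 each. No odds ratio per factor is stated.

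**Simulation.** 4,000 trials per scenario, 50% v 80% passage. Each trial fits a logistic model with treatment, size, location and four null covariates, keeps covariates with Wald p < 0.05, and refits with treatment forced in. Three inputs are assumptions: strata split 50/50, equal odds ratios for the two factors, and four null candidates. Average odds ratios are geometric means.

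| True odds ratio per factor | A given factor kept | Both kept | Stone-size odds ratio when kept |
|---|---|---|---|
| 1.5 | 14% | 3% | 3.3 |
| 2.0 | 30% | 9% | 3.8 |
| 2.12 | 33% | 12% | 3.9 |
| 3.0 | 59% | 35% | 4.7 |
| 4.5 | 82% | 68% | 6.1 |
| 6.0 | 91% | 83% | 7.8 |

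- If one factor carries the whole range (4.51) and the other has no effect, the first is kept in 86% of trials and the second in about 5%.
- With location split 30/70, it is kept in 27% of trials at odds ratio 2, 56% at 3 and 77% at 4.5.
- With 104 subjects and odds ratio 2, a given factor is kept in 34% of trials and both in 12%.

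**Separating selection from small-sample bias.** In a model with only treatment, size and location:

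| True odds ratio | Always included | Reported when kept by p < 0.05 | Ratio |
|---|---|---|---|
| 2.0 | 2.08 | 3.72 | 1.79 |
| 3.0 | 3.22 | 4.54 | 1.41 |
| 4.5 | 5.11 | 5.99 | 1.17 |

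At a true 6.0, the seven-term fit gives 7.9 without selection and 7.8 when kept, so selection adds nothing there.

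**Interval coverage when stone size is kept.** The 95% interval covers the truth in about 79% of trials at odds ratio 1.5 and 89-91% at 2. From 2.5-3 upward coverage is about nominal.

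**Null covariates.** If independent, at least one of four enters with probability 1 − 0.95⁴ = 18.5%. The simulation gives about 19-20%.

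**Treatment term.** With no true treatment effect, its rejection rate is 5.6-5.9% after selection, against 5.3-5.6% with fixed covariates.

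**The case against.** The strongest reply is that the rule governs a secondary model. Treatment is assessed by the Fisher test and by its own logistic model, and neither is selected from the data. A reader might infer that the treatment result is data-chosen; Section 13 does not support that, and the rejection rates above hardly move. This part of the reply stands and limits the point to the covariate findings.

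Three other strong readings also fail:

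- *The strata will usually be dropped.* This depends on odds ratios the documents do not give. Each factor is more likely dropped than kept only up to an odds ratio of about 2.5, and at 4 both are kept in 58% of trials. The 47-80% range fits either case, depending on how it divides between size and location.
- *Every retained odds ratio is inflated by selection.* The effect fades for strong factors. Treatment is not selected if it is forced in, as the adjustment for treatment group suggests.
- *The intervals are too narrow throughout.* Under-coverage is confined to weak and null covariates.

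It can also be said that a longer fixed covariate list would strain a model with about 31.5 expected non-passers. That stands too, and it argues for fixing only the strata. Section 12's list should not be borrowed, because it belongs to the pain analyses.

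None of this defends the rule itself. Followed as stated, it gives biased odds ratios for weak to moderate predictors and can omit the design factors.

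**Conclusion.** The point holds for the supporting multiple logistic model only. If each stratum factor has an odds ratio near 2, each is kept in roughly a third of trials or fewer. Its odds ratio when kept is then about 1.8 times what the same model gives without selection. At odds ratio 3 a factor is kept more often than not, but is still overstated by about 1.4 times on the same comparison. At 4.5 and above the problem is small.

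These sizes rest on the assumed odds ratios, the assumed strata split and the assumed candidate list. The direction of the bias for weak to moderate covariates does not depend on those choices. The primary conclusion about mirabegron is not at risk. The change should still be made, because it costs little and cannot credibly be made after unblinding.

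**What to change.** In Section 13, delete the sentence that makes inclusion depend on p < 0.05. State instead that the passage model always contains treatment, stone-size stratum (≤ 5 mm v > 5 mm) and location stratum (upper v lower ureter), and that this model is reported in full with 95% confidence intervals whatever the p-values. Label any screening of further covariates exploratory and report it separately from that model. Do not refer to Section 12 for the covariate list.

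The cost is a wording change before unblinding and two fixed parameters in a model of about 90 subjects. No data collection, visit or sample size changes.

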Subjects will be informed that they may also discontinue the study drug at any time if they would like to drop out of the trial and they may do so by contacting [name] or designee. Subjects will be informed to contact [name] or designee if they believe that they have passed their ureteral stone before discontinuing therapy. Subjects will be told to bring their medication bottles when they return to the clinic.

In the event that a subject has additional pain, discomfort, or other symptoms that may be related to their ureteral stone they may follow-up for an unscheduled visit to either the emergency department or the Urology clinic. The subject will be treated according to standard of care and information regarding their visit will be collected. If the subject must undergo an emergent procedure for their stone they will be determined to have failed therapy but will remain in the study to evaluate the study drug to reduce stent pain. Subjects that fail therapy early will undergo Visit 3 and will be evaluated at Visit 4 for the removal of their stent. Subjects will remain in the study for all outcome measurements if they do not require surgical intervention.

Interim Phone Follow-up #1 – (7 Days ± 3 days post-Visit 1)

The research study staff will contact the subject by phone approximately 7 days after Visit 1. Research staff will assess ureteral pain, medication/strainer compliance, and adverse events. Research staff will also identify whether or not the subject subjectively or objectively has passed their ureteral stone. The research staff will also answer any questions that the subject may have during this follow-up event.

Interim Phone Follow-up #2 – (21 Days ± 3 days post-Visit 1)

The research study staff will contact the subject by phone approximately 21 days after Visit 1. Research staff will assess ureteral pain, medication/strainer compliance, and adverse events. Research staff will also identify whether or not the subject subjectively or objectively has passed their ureteral stone. The research staff will also answer any questions that the subject may have during this follow-up event. The research staff will also remind the subjects to bring in their medication bottles to Visit 2 (see below).

Visit 2 – Urology Clinic (30 days ± 5 days post-Visit 1)

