14. END-POINTS

Endpoints will include spontaneous passage rate during the 30-day expectant management period or completion of the expectant management period without a requirement for surgery. Secondary endpoints will include ureteral pain during the expectant management period (Visit 1, Interim Follow-up #1 and #2, Visit 2) and pain with a ureteral stent in place (Visit 4).

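### The daily pain model (discrete time, unstructured matrix) is not reconciled with the four-contact pain endpoint, and no treatment contrast or degrees-of-freedom method is named

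*Combined protocol and SAP*

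**What the plan says.** Section 13 (Data Analysis) sets out the pain model in a few sentences. On the data: "The Wong Baker FACES pain scale will be measured daily for each patient". On the mean model: "The model will include fixed effects for treatment group, time (discrete) and a group-time interaction term". On the covariance: "The matrix of correlated residual terms will assume an unstructured format". The model is said to account for within-subject correlation and "will allow for all available data to be included in the model". Missing values are not imputed. The only remedies named for model problems are influence and residual diagnostics and data transformation.

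Section 14 (End-Points) defines the secondary endpoint as "ureteral pain during the expectant management period (Visit 1, Interim Follow-up #1 and #2, Visit 2", which is four contacts. Stent pain at Visit 4 is a separate endpoint there, and Section 13 gives it a separate USSQ model. Appendix A schedules FACES at the same four contacts and at Visit 4.

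On the window, Section 7 says "All subjects will then be followed for 30 days to determine the proportion of subjects with spontaneous passage", and the sentence beginning "Patients will record narcotic usage and pain scores during" refers to that same period. Section 9 heads Visit 2 as "Urology Clinic (30 days ± 5 days post-Visit 1", so the period can end between day 25 and day 35. The pain diary in Appendix B has 60 rows and is to be filled in daily until the patient returns to clinic.

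No section states which days enter the model, which term or contrast is the treatment comparison, which denominator degrees of freedom apply, or what replaces the unstructured matrix if it cannot be fitted.

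**The concern.** An unstructured matrix with discrete time is a sound choice for a handful of visits. Applied to daily scores, the number of covariance parameters grows with the square of the number of days, while the number of patients stays at about 100. Tests with many numerator degrees of freedom then depend heavily on the small-sample correction, and the plan names none.

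The two sections also give different analyses of one endpoint. Read from Section 14, the model has four times. Read from Section 13 over the expectant period, it has about 30. The group-time interaction is the only treatment-by-time term named, and Section 13 tests secondary outcomes at 0.05 two-sided without adjustment for multiple comparisons. A reader of the results could not tell from the plan whether a reported p-value came from a well-calibrated test.

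**Working it through.** **Inputs.** Section 11 gives 45 per group, so 2 × 45 = 90 patients, and 104 enrolled to allow for 15% attrition. Allocation is 1:1 (Section 7). Section 13 gives daily or, through Section 14, four-contact times. The expectant period is 30 days (Section 7). The plan states no figure for the pain model, so there is none to reproduce.

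**Step 1: size of the matrix.** An unstructured matrix over T times has T(T+1)/2 parameters.
- T = 4: 4 × 5 / 2 = 10.
- T = 30: 30 × 31 / 2 = 465, or 465/104 = 4.5 per enrolled patient and 465/90 = 5.2 per patient at 90.

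With complete diaries the 30-day matrix can still be estimated: it needs at least T + 2 = 32 patients.

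**Step 2: error rate of the group-time test.** With complete multivariate-normal data and a REML unstructured matrix, the group-time Wald statistic is Hotelling's T² with p = T − 1 and ν = N − 2. Exactly, T²(ν − p + 1)/(νp) follows F(p, ν − p + 1). An analyst using an ordinary reference would reject when T² exceeds the 95% point of chi-square(p), or p times the 95% point of F(p, ν). The true rejection rate under no effect is the exact F tail beyond the rescaled cut-off.

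Worked case, N = 104 and T = 30: p = 29, ν = 102, ν − p + 1 = 74.
- Chi-square cut-off 42.56. Rescaled: 42.56 × 74/(102 × 29) = 1.065. P(F(29,74) > 1.065) = 0.402.
- F(29,102) cut-off 1.579, so T² = 29 × 1.579 = 45.78. Rescaled: 45.78 × 74/(102 × 29) = 1.145. P(F(29,74) > 1.145) = 0.314.

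| N | Times | Exact reference | Rejects, F(p, N−2) | Rejects, chi-square |
|---|---|---|---|---|
| 104 | 30 | F(29,74) | 31.4% | 40.2% |
| 90 | 30 | F(29,60) | 38.1% | 48.4% |
| 104 | 4 | F(3,100) | 5.4% | 6.0% |
| 90 | 4 | F(3,86) | 5.4% | 6.1% |

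No pain means, variances or correlations are needed: under no effect the distribution does not depend on them. It does depend on normality and complete diaries. Using the exact reference in the third column gives 5%.

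**Step 3: the averaged contrast.** The group difference averaged over days has one numerator degree of freedom. With complete data it is a two-sample t-test on patient means, exact at 5% with N − 2 df. Even against chi-square(1), the rate is P(F(1,102) > 3.84) = 5.3% with 104 patients and 5.3% with 90.

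**The case against.** **The inflated test is not named as the treatment test.** Section 13 lists the interaction among the fixed effects, but its stated purpose is to compare pain between groups. A reader might infer that the plan will produce false positives in 31% to 48% of trials. The documents do not support that. It needs three things together: daily time levels, the 29-df interaction used for inference, and an uncorrected reference distribution. Silence on degrees of freedom is not a choice of the wrong method. This objection stands, and the rates are given here as what could happen.

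**The Section 14 reading is nearly harmless.** Four contacts give 10 parameters and 5.4% to 6.1%. That is true, but Section 13 commits in words to daily scores, and nothing says that Section 14 overrides it.

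**The exact reference would cure the daily test.** It would, for complete data. That is a reason to name the method. It does not settle the time points or the contrast.

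**Two further readings go too far.** A reader might infer from the 60-row diary that the model spans 60 days and could not be fitted. No section says that all 60 rows enter it, and Sections 13 and 14 keep stent pain separate. A reader might also infer that the choices would be made after seeing results. The trial is double-blind, and nothing in the documents shows that.

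**Conclusion.** The concern holds as a gap in specification with a possible, sizeable effect on one test. Sections 13 and 14 describe different time points for one endpoint, and no contrast, degrees-of-freedom method or fallback covariance is given. The daily interaction test, used without a small-sample correction, could run at 31% to 40% with 104 patients or 38% to 48% with 90. Four times, or a single averaged contrast, are close to nominal. These figures assume complete multivariate-normal data over days 1 to 30; incomplete diaries were not sized. The matter is confined to one secondary endpoint of a Phase 2 trial. The primary Fisher test and the sample size are untouched. It should be corrected, because the remedy costs little.

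**What to change.** Amend Section 13, and align Section 14 with it, as follows.

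1. Limit the expectant-period pain model to days 1 to 30.
2. Replace the 30 daily levels with four time blocks. One option is weekly diary means (days 2–8, 9–15, 16–22 and 23–30, averaging the recorded entries). The other is the Section 14 contacts. If the contacts are chosen and Visit 1 becomes a covariate, three responses remain (3 × 4 / 2 = 6 parameters).
3. Keep the unstructured matrix (10 parameters for four blocks) with Kenward-Roger degrees of freedom.
4. Name the group difference averaged over the blocks as the treatment contrast, with the group-time term supportive.
5. Adjust for Visit 1 pain and for the stone-size and stone-location strata from Section 8. Section 12 lists size and location only as possible covariates.
6. Give one fallback covariance with its df method, for example heterogeneous Toeplitz, also with Kenward-Roger.
7. Reconcile Section 7, the Section 9 text (unscheduled visits, Visit 2, early completion), Section 14 and Appendix B on which days pain is recorded and analysed. Cover entries after stone passage or an early procedure.

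The cost is SAP wording and a sentence on recording. The diary, Visit 1 score and strata are already collected, although patients who pass early may have to keep the diary longer than they otherwise would. Visit 1 adjustment lowers the variance of the group difference by about the squared correlation (9% at an assumed 0.3, 25% at an assumed 0.5). The downsides are less day-level detail and a week-4 mean that covers fewer days for patients seen early in the Visit 2 window: three days (23–25) if seen on day 25, against eight (23–30).
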